- 2. Missing data in patients who completed the main 6-month treatment period will be imputed separately, using a model estimated solely from data observed in other patients who completed the main 6-month treatment period and have the measurement for the primary endpoint at Week 26. Since in general, the missing pattern will not be monotone, a two-step approach will be used:
- Step 1: the Markov Chain Monte Carlo (MCMC) method will be used in conjunction with the IMPUTE=MONOTONE option to create an imputed data set with a monotone missing pattern. The imputation model will include the continuous fixed covariates of the baseline HbA1c value as well as the changes from baseline in HbA1c at Week 12 and Week 26.
- Step 2: using the monotone data set from step 1, missing data will be imputed using the regression method. The imputation model will include the fixed categorical effects of the treatment group, the randomization strata geographical region and type of diabetes (Europe T1DM, US T1DM, US T2DM, Japan T1DM), screening HbA1c (<8%, ≥8%) (except when analyzing the change in HbA1c) and prior use of NovoLog/NovoRapid (Yes, No), as well as the continuous fixed covariates of the baseline HbA1c value and the changes from baseline in HbA1c at Week 12 and Week 26.

Missing values will be imputed 10 000 times. Completed datasets from the two parts detailed above will be combined into a single dataset. Each completed dataset will be analyzed using an analysis of covariance (ANCOVA) of the change in HbA1c from baseline to Week 26, including the fixed categorical effects of treatment group (SAR341402, NovoLog/NovoRapid), the randomization strata geographical region and type of diabetes (Europe T1DM, US T1DM,

US T2DM, Japan T1DM), screening HbA1c (<8%, $\ge8\%$) (except when analyzing the change in HbA1c) and prior use of NovoLog/NovoRapid (Yes, No), as well as the continuous fixed covariate of baseline value. Results from the 10 000 analyses will be combined using Rubin's formula.

The adjusted least squares (LS) mean of the change in HbA1c from baseline to Week 26 for each treatment group (SAR341402, NovoLog/NovoRapid) will be estimated, as well as the between-group LS mean difference of SAR341402 versus NovoLog/NovoRapid, with the corresponding standard errors and 2-sided 95% CIs.

Non-inferiority will be demonstrated if the upper bound of the 2-sided 95% CI of the difference between SAR341402 and NovoLog/NovoRapid on the ITT population is <0.3%.

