11.4.2.1.4 Additional analysis

Analyses on the primary efficacy endpoint will be presented for the subgroups comparing SAR341402 with NovoLog in patients randomized in the US (approximately 330 patients, 230 with T1DM and 100 with T2DM) and comparing SAR341402 and NovoRapid in regions using NovoRapid (approximately 250 patients with T1DM). The analysis will be performed using a similar multiple imputation approach in two parts, as for the primary efficacy endpoint, followed by a similar ANCOVA model (as described in Section 11.4.2.1.1) adding the corresponding subgroup factor and subgroup factor-by-treatment interaction. The randomization strata of geographical region (Europe, Japan, US) and Type of diabetes (T1DM, T2DM) will not be included in the model.

Property of the Sanofi Group - strictly confidential

13-Dec-2017 Version number: 1

Least square means difference of SAR341402 versus NovoLog and SAR341402 versus NovoRapid at Week 26 will be provided, as well as the corresponding SEs and 95% CI, within each subgroup. The significance level of the treatment-by-subgroup factor interaction term will also be provided for descriptive purpose. Forest plots will be provided.

Additionally, the James-Stein (J-S) shrinkage estimator may be used to evaluate the treatment effect in each subgroup defined by type of comparator, with a different approach (15). This estimate is derived from the overall and subgroup treatment effect estimates in order to use all study information (including information collected in the other subgroup). Details will be provided in the statistical analysis plan.

Explorative analyses will be performed on the primary endpoint to summarize the treatment effects across subgroups defined by baseline and screening factors, such as: category of age (<65, [65 to 75] and ≥75 years of age), baseline BMI (<30 and ≥30 kg/m²), randomization strata (geographical region [Europe, US, Japan], type of diabetes [T1DM, T2DM], screening HbA1c categories [<8%, ≥8%] and prior use of NovoLog/NovoRapid [Yes, No]) and type of comparator (NovoLog and NovoRapid). Subgroup analyses will be detailed in the SAP.

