Missing data in patients who completed the main 6-month treatment period will be imputed separately, using a model estimated solely from data observed in other patients who completed the main 6-month treatment period and have the measurement for the primary endpoint at Week 26. Since in general, the missing pattern will not be monotone, a two-step approach will be used:

- Step 1: the Markov Chain Monte Carlo (MCMC) method will be used in conjunction with the IMPUTE=MONOTONE option to create an imputed data set with a monotone missing pattern. The imputation model will include the continuous fixed covariates of the baseline HbA1c value as well as the changes from baseline in HbA1c at Week 12 and Week 26.
- Step 2: using the monotone data set from step 1, missing data will be imputed using the regression method. The imputation model will include the fixed categorical effects of the treatment group, the randomization strata of geographical region and type of diabetes (Europe T1DM, US T1DM, US T2DM, Japan T1DM) and prior use of NovoLog/NovoRapid (Yes, No), as well as the continuous fixed covariates of the baseline HbA1c value and the changes from baseline in HbA1c at Week 12 and Week 26.

Missing values will be imputed 10,000 times. Completed datasets from the two parts detailed above will be combined into a single dataset. Each completed dataset will be analyzed using an analysis of covariance (ANCOVA) of the change in HbA1c from baseline to Week 26, including the fixed categorical effects of treatment group (SAR341402, NovoLog/NovoRapid), the randomization strata of geographical region and type of diabetes (Europe T1DM, US T1DM, US T2DM, Japan T1DM) and prior use of NovoLog/NovoRapid (Yes, No), as well as the continuous fixed covariate of baseline value. Results from the 10,000 analyses will be combined using Rubin's formula (MIANALYZE procedure in SAS).

Statistical Analysis Plan SAR314102-EFC15081 - insulin aspart 28-Feb-2018 Version number: 1

The adjusted least squares (LS) mean of the change in HbA1c from baseline to Week 26 for each treatment group (SAR341402, NovoLog/NovoRapid) will be estimated, as well as the between-group LS mean difference of SAR341402 versus NovoLog/NovoRapid, with the corresponding standard errors and 2-sided 95% CIs. These values will be calculated using the observed proportions of patients in the randomization strata and the observed baseline mean HbA1c in the ITT population.

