2.4.4.1.4 Subgroup analyses

The primary efficacy endpoint will be further analyzed to examine whether the treatment effect varies in subgroups defined by the following baseline covariates:

- Race (American Indian or Alaska Native, Asian, Black or African American, Native Hawaiian or Other Pacific Islander, White, More than One Race, Unknown or Not Reported),
- Ethnicity (Hispanic or Latino, Not Hispanic or Latino, Unknown /Not Reported),
- Age group (<65, \geq 65 to <75, \geq 75 years of age),
- Sex (male, female),
- Baseline BMI ($<30, \geq 30 \text{ kg/m}^2$),
- Baseline estimated GFR categories (<60, ≥60 mL/min/1.73m²),
- Randomization stratum of type of diabetes (T1DM, T2DM),
- Randomization stratum of screening HbA1c (< 8.0%, $\geq 8.0\%$),
- Randomization stratum of prior use of NovoLog/NovoRapid (Yes, No),
- Type of comparator (NovoLog, NovoRapid),
- Regions (North America, Western Europe, Eastern Europe, ROW),
- Duration of diabetes ($<10, \ge 10$ years).

The treatment effect across the subgroups defined above will be estimated for the primary efficacy variable (change in HbA1c from baseline to Week 26) in the ITT population and separately for the T1DM patients, using all post baseline HbA1c data available during the main 6-month randomized period. The same multiple imputation approach as described for primary analysis will be applied, using the 10,000 completed datasets generated for the primary analysis. Each completed dataset will be analyzed using an ANCOVA of change from baseline to Week 26 in HbA1c, including the fixed categorical effects of treatment group (SAR341402, NovoLog/NovoRapid), the randomization stratum of prior use of NovoLog/NovoRapid (Yes, No), the corresponding subgroup factor and subgroup factor-by-treatment interaction, and the continuous fixed covariate of baseline value. The randomization strata of geographical region and type of diabetes (Europe T1DM, US T1DM, US T2DM, Japan T1DM) will not be included in the model. Results from the 10,000 analyses will be combined using Rubin's formula (MIANALYZE procedure in SAS).

When the subgroup considered is the randomization stratum of screening HbA1c ($<8.0, \ge8.0\%$), the baseline HbA1c value will be removed from the model.

When the subgroup considered is the randomization stratum of prior use of NovoLog/NovoRapid (Yes, No), the randomization stratum of prior use of NovoLog/NovoRapid (Yes, No) will be included only once in the model (as subgroup factor).

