2.4.5.1 Analyses of Hypoglycemia

All analyses of hypoglycemia will be performed on the safety population and for the T1DM patients (except for analyses monthly, by time of the day and by subgroup), separately on events occurring during the main 6-month on-treatment period and during the 12-month on-treatment period (as defined in Section 2.1.4).

Incidence of patients with at least one hypoglycemia

- Incidence of patients with at least one hypoglycemia will be presented by treatment group for any hypoglycemia and for each hypoglycemia category (as described in Section 2.1.4.1).
- For any hypoglycemia, severe and documented symptomatic hypoglycemia category, incidence of patients with at least one hypoglycemia will be compared for SAR341402 versus NovoLog/NovoRapid using a logistic regression method. The model will include fixed-effect terms for treatment group, the randomization strata of geographical region and type of diabetes (Europe T1DM, US T1DM, US T2DM, Japan T1DM), screening HbA1c (<8%, ≥8%), and prior use of NovoLog/NovoRapid (Yes, No). If the logistic model does not converge (e.g., due to sparse data), randomization strata may be adapted or removed from the model. Odds-ratios and 95% CIs will be displayed using forest plots.
- Incidence of patients with at least one severe hypoglycemia will be summarized by symptom.
- The number of severe hypoglycemia and the number of documented symptomatic hypoglycemia <3.0 mmol/L (54 mg/dL) per patient will be summarized by treatment group.
- For any hypoglycemia, severe and documented symptomatic hypoglycemia category, incidence of patients with at least one hypoglycemia will be summarized by time of the day. Histograms will be provided.
- For any hypoglycemia, severe and documented symptomatic hypoglycemia category, incidence of patients with at least one hypoglycemia will be presented by subgroup and compared between SAR341402 and NovoLog/NovoRapid using a similar logistic regression model as described above, with added fixed-effect terms for the subgroup and the subgroup-by-treatment interaction. When the subgroup considered will be equal (or close) to one of the randomization strata, this randomization stratum will be removed from the model. Odds-ratios and 95% CIs will be presented across subgroups using forest plots. The significance level of the subgroup-by-treatment interaction will be also provided for descriptive purpose. The following subgroups will be displayed:

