2.4.5.7 Analyses of anti-insulin antibody data

The analyses of immunogenicity data will be descriptive (no formal statistical testing) and based on the AIA population. Separate analyses will be performed for the T1DM and T2DM patients. Analyses will be presented separately for the main 6-month and the 12-month on-treatment periods.

For T1DM patients, all analyses of immunogenicity will be produced except for analyses by subgroups defined by baseline and screening factors. Analyses by type of comparator (NovoLog, NovoRapid) will be produced.

For T2DM patients, the following analyses will be produced:

- Summary of AIA response,
- Summary of AIAs by visit,
- Summary of AIA response by prior NovoLog/NovoRapid (Yes, No),
- Summary of change in HbA1c (%) from baseline to Week 26 by treatment-emergent AIA,
- Summary of change in insulin dose (mealtime, basal, total daily) from baseline to Week 26 by treatment-emergent AIA,
- Scatterplot analyses to assess the relationship between immunogenicity endpoints and efficacy/safety assessments,
- Boxplots of maximal AIA titer.

Anti-insulin antibody response

The number and percentage of patients will be provided by treatment group for each of the following categories:

- Patients with treatment-induced AIAs,
- Patients with treatment-boosted AIAs,
- Patients with treatment-emergent AIA (AIA incidence),
- Patients without treatment-emergent AIA,
- Patients with pre-existing AIAs or treatment-induced AIAs (AIA prevalence).

For exploratory purposes, the difference between SAR341402 and NovoLog/NovoRapid in the percentage of patients with treatment-emergent AIAs (AIA incidence) will be provided with associated 2-sided 90% CI. Patients with inconclusive results will not be part of the analysis. Results will be obtained by fitting a binomial regression model with an identity-link function. The model will include fixed categorical effects for treatment, the randomization strata of geographical region and type of diabetes (Europe T1DM, US T1DM, US T2DM, Japan T1DM), screening HbA1c (<8%, \geq 8%), and prior use of NovoLog/NovoRapid (Yes, No). The risks within each treatment group and risk difference will be provided with their 90% CIs using the adjusted LS mean estimates of the treatment effect.

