Exploratory analyses will be performed by subgroups defined by baseline and screening factors.

The following subgroups will be displayed:

- Race (American Indian or Alaska Native, Asian, Black or African American, Native Hawaiian or Other Pacific Islander, White, More than One Race, Unknown or Not Reported),
- Ethnicity (Hispanic or Latino, Not Hispanic or Latino, Unknown /Not Reported),
- Age group (<65, \geq 65 to <75, \geq 75 years of age),
- Sex (male, female),
- Baseline BMI (<30, ≥ 30 kg/m²),
- Baseline estimated GFR categories ($<60, \ge 60 \text{ mL/min}/1.73 \text{ m}^2$),
- Randomization stratum of type of diabetes (T1DM, T2DM),
- Randomization stratum of screening HbA1c (<8%, $\geq8\%$),
- Randomization stratum of prior use of NovoLog/NovoRapid (Yes, No),
- Type of comparator (NovoLog, NovoRapid),
- Regions (North America, Western Europe, Eastern Europe, ROW),
- Duration of diabetes ($<10, \ge 10$ years),
- Anti-SAR341402/NovoLog/NovoRapid antibody status at baseline (Positive, Negative).

Further subgroup analyses may be performed if deemed necessary for interpretation of results.

Relationship between immunogenicity endpoints and efficacy/safety assessments

Subgroup analyses and scatterplots will be conducted to assess the relationship between immunogenicity endpoints and efficacy/safety assessments.

The following efficacy/safety assessments will be summarized by treatment-emergent AIA (Yes, No) and treatment-emergent AIA at last on-treatment value (Yes, No):

- Primary efficacy endpoint (change in HbA1c from baseline to Week 26) (for the main 6-month analyses) and change in HbA1c from baseline to Week 52 (for the 12-month analyses): same statistical model as described in Section 2.4.4.1.4 for subgroup analyses will be performed.
- Hypoglycemia (any, severe, documented symptomatic): the proportion of patients with at least one event will be compared between treatment groups using the same statistical model as described in Section 2.4.5.1 for hypoglycemia subgroup analyses. The number of severe hypoglycemia and the number of documented symptomatic hypoglycemia <3.0 mmol/L (54 mg/dL) per patient will also be displayed for each treatment group.
- Common TEAEs: descriptive statistics by primary SOC, HLT, and PT, showing number (%) of patients sorted by SOC internationally agreed order. The other levels (HLT, PT) will be presented in an alphabetic order.

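### The HbA1c subgroup ANCOVA drops the region-by-diabetes-type strata for every factor, and continuous baseline HbA1c for the screening-HbA1c factor, giving up modest precision and comparability with the primary model without a stated reason

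*SAP*

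**What the plan says.** SAP 2.4.4.1.4 fits treatment, prior use of NovoLog/NovoRapid, the subgroup factor, its interaction with treatment, and baseline HbA1c. It then states, without limiting this to particular factors: "The randomization strata of geographical region and type of diabetes (Europe T1DM, US T1DM, US T2DM, Japan T1DM) will not be included in the model". When the factor is the screening-HbA1c stratum, "the baseline HbA1c value will be removed from the model".

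Other sections of the two documents differ:

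- **Primary ANCOVA (SAP 2.4.4.1.1):** includes the four-level strata, "as well as the continuous fixed covariate of baseline value". The return-to-baseline and per-protocol ANCOVAs (2.4.4.1.2, 2.4.4.1.3) have the same terms.
- **James-Stein comparator models (SAP 2.4.4.1.5):** keep diabetes type within the NovoLog subgroup and region within the NovoRapid subgroup.
- **SAP 2.5.6:** says in general terms that the region stratum is part of the models.
- **Hypoglycemia subgroups (SAP 2.4.5.1):** "When the subgroup considered will be equal (or close) to one of the randomization strata, this randomization stratum will be removed from the model".
- **Protocol 11.4.2.1.4:** "The randomization strata of geographical region (Europe, Japan, US) and Type of diabetes (T1DM, T2DM) will not be included in the model". This sentence belongs to the comparison by type of comparator. The same section leaves the remaining subgroup analyses to the SAP.
- **Protocol 11.4.2.1.1:** uses the screening-HbA1c stratum "except when analyzing the change in HbA1c", so screening category and baseline HbA1c are not used together in an HbA1c model.

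**The concern.** There are two separate omissions.

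**Strata.** For the comparator factor, region is determined by the factor (NovoLog in the US, NovoRapid elsewhere), so leaving it out is understandable. For sex, age, BMI, eGFR, ethnicity, diabetes duration, prior use or screening HbA1c there is no such aliasing, and no reason is given for extending the rule.

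**Baseline HbA1c.** A two-level split at 8% carries only part of the information in the continuous value. Adjustment within each category is lost exactly where the subgroup is defined by glycaemic level.

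At stake is the width of the subgroup and interaction intervals, and whether the forest plots can be read beside the primary estimate without part of a difference coming from the covariate set. The same model is reused for HbA1c change by treatment-emergent antibody status in SAP 2.4.5.7 ("same statistical model as described in Section 2.4.4.1.4 for subgroup analyses will be performed").

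**Working it through.** **Plan's own figure.** The documents give no figure for the subgroup models. The primary power reproduces and does not depend on them: SE = 1.0 × √(2/290) = 0.0830; 0.3/0.0830 − 1.96 = 1.65; power 95.1% (stated: at least 95%). Both directions: 2 × 0.9508 − 1 = 90.2% (stated: at least 90%).

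**Inputs from the documents.** SD 1.0%; US T1DM 230, US T2DM 100, non-US T1DM 250; screening HbA1c limited to 7–10%.

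**Inputs assumed.** Screening HbA1c normal, mean 8.0, SD 0.8, truncated to 7–10; baseline = screening + noise of SD 0.25; slope of change on baseline −0.3 to −0.6; Europe/Japan split 190/60 (also 220/30); stratum means 0 to 0.6% HbA1c apart; 1.0% read as the total SD of change.

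**Baseline variance the split leaves unexplained.** Truncated-normal moments give a screening variance of 0.422, of which 0.146 lies within the two categories. Adding noise variance 0.0625: (0.146 + 0.0625)/(0.422 + 0.0625) = 0.209/0.484 = 43%. With noise SD 0 the share is 35%; with noise SD 0.35 it is 49%.

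**SE ratio, upper corner.** Slope −0.6; stratum effects 0, 0.2, 0.2, −0.4 for Europe, Japan, US T1DM, US T2DM.

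- Stratum variance: (60 × 0.04 + 230 × 0.04 + 100 × 0.16)/580 − (18/580)² = 0.0476 − 0.0010 = 0.0466.
- Full-model residual variance: 1 − 0.36 × 0.484 − 0.0466 = 0.779.
- Within-category baseline term: 0.36 × 0.209 = 0.075.
- Both dropped: √((0.779 + 0.075 + 0.0466)/0.779) = 1.075.
- Baseline alone: √((0.779 + 0.075)/0.779) = 1.047.
- Strata alone: √((0.779 + 0.0466)/0.779) = 1.030.

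**Lower corner.** Slope −0.3, no stratum effect: residual 1 − 0.09 × 0.484 = 0.956; ratio √((0.956 + 0.09 × 0.209)/0.956) = 1.010. Dropping the strata then costs nothing.

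**If 1.0% is a residual SD**, upper corner: √(1 + 0.075 + 0.0466) = 1.059 for both; 1.037 for baseline alone; 1.023 for strata alone.

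**Simulation** (stratified randomisation, no missing data), percentage change in SE, reduced against full model:

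| Factor | Terms dropped | SE change |
|---|---|---|
| Screening HbA1c | both | +0.8 to +7.6% |
| Screening HbA1c | baseline only | +0.9 to +4.8% |
| Screening HbA1c | strata only | 0 to +3.0% |
| Sex-like | strata | −0.2 to +2.9% |
| BMI-like | strata | −0.2 to +2.6% |
| Age-like | strata | −0.2 to +2.7% |
| Race-like (Asian/Japan) | strata | −1.0 to +2.8% |
| Diabetes type | region | 0 to +0.5% |

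The interaction SE inflates by the same proportion. T1DM-only analyses give +0.9 to +7.3% (screening HbA1c, both dropped) and −0.1 to +2.6% (sex-like). A second simulation with slopes −0.2 to −0.6 gave 0.6 to 7.1% for both terms dropped.

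**In patients.** 1 − 1/1.009² = 1.8%; 1 − 1/1.076² = 13.6%. The range is thus equivalent to losing about 2 to 14% of the subgroup's patients.

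**Shift of the estimate.** Mean absolute difference between reduced and full model: 0.011–0.029% HbA1c (screening HbA1c, both dropped) and 0.003–0.016% (sex-like), against subgroup SEs of about 0.10–0.12. Mean estimates were within 0.024 of the true zero, small subgroups included.

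**The case against.** The strongest reply is that this is a modelling preference. The subgroup model is fully prespecified, the protocol delegates it to the SAP, the one subgroup model the protocol does specify omits the same strata, and the interaction test is descriptive. All of that is correct, and it rules out reading the SAP as contradicting the protocol. It does not supply a reason for carrying the omission to factors that do not overlap the strata.

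Three narrower objections stand and limit the point:

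- **The hypoglycemia rule concerns strata only.** That model has no continuous baseline HbA1c, so the rule cannot be used to argue for keeping it here. The protocol and SAP 2.4.4.2.1 avoid having both HbA1c terms in one model, so removing baseline follows a convention of the documents. The case for keeping it rests on precision and consistency with the primary ANCOVA.
- **The sizes are assumed.** The upper end needs the steepest slope and the widest stratum spread together. With a 0.3-point spread, the strata alone cost about 0.6–0.7%.
- **Keeping strata is not always better.** Asian race and the Japan stratum nearly coincide, and omission can then be up to 1% more precise.

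A reader might also infer that the antibody-status analysis is confounded by diabetes type. SAP 2.4.5.7 already answers much of this: "Separate analyses will be performed for the T1DM and T2DM patients". Antibody status arises after randomisation, so that analysis is descriptive under either model.

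**Conclusion.** The point holds as a minor improvement. The SAP generalises a protocol rule written for one overlapping factor, and separately replaces a continuous covariate with a two-level category, in both cases departing from its own primary model without explanation. The loss is about 1 to 7.6% in SE for the screening-HbA1c subgroups (ceiling about 6% on the residual-SD reading), and about 0 to 3% from the strata for other factors, zero if strata do not affect HbA1c change. These are illustrations under assumed slopes, stratum effects and HbA1c distribution.

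A reader might infer that the subgroup estimates are biased or that the non-inferiority conclusion is weakened. The documents do not support either. Randomisation is stratified, and treatment is independent of baseline covariates within a subgroup defined at baseline. The primary test, its alpha and its power use a different model that keeps both terms.

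**What to change.** In SAP 2.4.4.1.4, specify:

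- The subgroup model is the primary ANCOVA (treatment, region-by-diabetes-type strata, prior use, continuous baseline HbA1c) plus the subgroup factor and its interaction with treatment.
- Only the stratum component equal or close to the factor is removed. For diabetes type, keep region. For Regions, keep diabetes type. In T1DM-only analyses the strata term is region alone. For race, the region component may be dropped or collapsed.
- Continuous baseline HbA1c stays in the screening-HbA1c model, with LS means at each category's own mean baseline. Evaluating both categories at the overall mean would describe each away from its own centre. The treatment difference does not depend on this choice, because baseline does not interact with treatment in the model.
- The type-of-comparator model stays as Protocol 11.4.2.1.4 states it; SAP 2.4.4.1.5 already gives a comparator analysis adjusted for the remaining strata. If the comparator model is changed, record it in SAP 1.6.

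Through SAP 2.4.5.7 the same wording would carry over to the antibody-status analysis. The cost is a few lines of SAP text, slightly different terms by factor, and up to about 1% in SE where a factor is nearly collinear with region and the stratum is kept. The same 10,000 imputed datasets serve, and no protocol change is needed. If the sponsor prefers the present model, one sentence giving the reason would close the point.
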